### 6.3 MRI/MRS/fMRI studies

Subjects are instructed to fast for 7-8 hours prior to the 1H MRS examination. Data from MRI/MRS/fMRI studies is obtained using either 1.5 Tesla – or 3.0 Tesla system (Intera, Philips Medical Systems, Best, the, Netherlands).

### 6.3.1 Liver, adipose tissue, and myocardium

#### Liver studies

Axial T1-weighted dual fast field echo images (TE 2.3 and 4.6 ms, TR 120 ms, slice thickness 10 mm without gap), covering the area of the liver are acquired during standardized breath-hold instructions. A MR imager (Gyroscan Intera CV Nova Dual, Philips Medical Systems, the Netherlands or Magnetom Verio, Siemens Medical Systems, Germany) with a flexible surface coil and body coil is used for liver volume and tiglyceride content measurement. A single voxel with a volume of 27 cm^3 is positioned in the liver outside the area of the great vessels. To ensure similar voxel placement before and after the intervention, the voxel location is recorded in each patient. A PRESS 1H MRS sequence is used with the following parameters: TR = 3000 ms, TE = 25 ms with data acquired during breath-hold intervals. 1H MRS findings of the liver have been validated in both animal and human studies (87,88)(89). Using a local workstation, liver margins are outlined manually on each individual image. Total liver volume is calculated by multiplying the measured surface areas of each slice by the slice thickness, as previously described (89).

#### Adipose tissues

Additionally T1W FFE images are obtained at the level of the intervertebral disc L2-L3 for analysis of abdominal adipose tissue masses as previously described (90) and to obtain anatomical reference for PET. Thigh area is scanned for the anatomical reference for PET.

#### Myocardium

Mediastinal fat is analysed from thoracal image. Heart function is imagined as in routine clinical heart-studies: Left ventricular function and dimensions are measured from continuous short axis

slices by using the balanced turbo field echo (bTFE) sequence on 1.5 T or 3.0 T MRI-system (91). Ten to fourteen slices are acquired during serial breath holds and vectorcardiographic (VCG) or electrocardiographic (ECG) gating to cover the left ventricle completely from apex to atrium. Slice thickness is 6-8 mm without gap between slices. Imaging parameters are set depending of used MRI-unit, for 1.5 T MRI these are e.g. repetition time (TR) of 3.4 ms, echo time (TE) of 1.7 ms, flip angel of 60° and matrix of 256 x 256. Images are stored digitally in DICOM-format. Afterwards, when all subjects have undergone MRI-scan, image analysis is performed using validated post-processing software (e.g. ViewForum R5.1; Philips Medical Systems) and validated analysis method (92). Cine loops of every slice are reviewed to identify end-diastolic and end-systolic frames. Epicardial and endocardial contours are outlined manually. Papillary muscles are separately outlined and included in myocardium. End-diastolic volume (EDV) and end-systolic volume (ESV) are calculated from which cardiac output (CO), stroke volume (SV) and ejection fraction (EF) are computed. Myocardial mass is calculated from diastolic images. In addition triglyceride content in myocardium will be studied as previously reported(93)

#### **Echocardiography**

A Vivid 7 (GE Vingmed Ultrasound AS, Horten, Norway) ultrasound equipment will be used for cardiac measurements. The subjects will be lying in left recumbent position throughout the study.

The standard tomographic views of the left ventricle (parasternal long- and short-axis and apical 4chamber, 2-chamber, and long-axis views) are obtained. LV and RV diameters, LV wall thickness and left atrial diameter are measured from M-mode tracings in the parasternal long axis as done routinely.

Using pulsed-wave Doppler, mitral inflow velocities (peak early diastolic velocity (E), peak late diastolic velocity (A), E/A ratio, and isovolumetric relaxation time (IVRT)) and pulmonary vein flow velocities are measured. With tissue Doppler imaging, longitudinal myocardial velocity and deformation are measured by use of strain rate and strain calculations. Apical long-axis and parasternal short-axis imageloops are acquired with frame rate over 60 Hz to be able to do speckle tracking with off-line analysis software. With speckle tracking radial and longitudinal myocardial velocities and deformations are calculated. All calculations and the most of the measurements are done afterwards with standard analysis software (EchoPac PC, GE Vingmed Ultrasound AS, Horten, Norway). Each representative value is obtained from the average of three measurements.

### 6.3.2 Brain

The following conventional image sequences are acquired: (1) sagittal T1-weighted sequence (TR/TE 650/15 [repetition time/echo time msec]), (2) coronal fluid attenuated inversion recovery (FLAIR) sequence (TR/TE/TI 11000/140/2800 [repetition time/echo time/inversion time msec]), (3) transverse T2-weighted spin-echo sequence (TR/TE 4500/100 [repetition time/echo time msec]). All these sequences are acquired with slice thickness of 5 mm and 1 mm interslice gap. Moreover a transverse T1-weighted turbo gradient-echo sequence (TR/TE 25/4.6 msec, flip angle of 30°, contiguous sections and section thickness of 1 mm) is obtained. Cerebral white matter signal intensity changes are rated on FLAIR images by using the scale proposed by Fazekas et al (92), which has a maximum score of 6 and has shown a "very good" inter-observer reproducibility in a prior study (94).

### 6.3.2.1 Brain diffusion tensor imaging (DTI)

For DTI, 32 non-colinear directions of gradients are acquired to obtain the whole diffusion tensor with an echo-planar imaging (EPI) single-shot sequence. Diffusion imaging acquisition parameters

are as follows: TE/80 ms, 30 ms, 45 ms, 32 transverse slices, slice thickness 5 mm with a gap of 0.5 mm. ROIs are placed individually for each patient by one experienced neuroradiologist blinded to the diagnosis of morbid obesity. Contamination of adjacent structures and T2-visible focal lesions are avoided. ROI:s are placed in the following areas bilaterally: frontal, parietal, occipital white matter as well as middle thalamus, pulvinar and putamen. ROIs are also placed in the genu and splenium of corpus callosum. The FA and MD values of each ROI are measured by using Pride software (Philips Medical Systems, Best, The Netherlands). Brain volume index (BVI) is calculated from MD maps by dividing the brain volume by the sum of brain volume and cerebrospinal fluid (CSF) volume. Brain tissue and CSF are separated by using a threshold value of 2.4 x 10-3 mm2/s i.e. pixels with MD value of 2.4 x 10-3 mm2/s or more were considered as CSF.

## 6.3.2.2 Functional MRI (fMRI) studies

The aim of the fMRI is to assess how bariatric surgery (sleeve/bypass) influences the brain reward system response to food stimuli. The main interest is whether bariatric surgery can specifically reduce the responses to appetizing, high-calorie foods and is there a difference in responses between the two surgical procedures. Reward drive will be measured using BIS/BAS-questionnaire. Self-reported hunger level will be measured with a visual analogue scale, and food craving with the Food Craving State / Trait (FCS-FCST) questionnaire (31). Before a control subject can participate in the fMRI study block, the possible factors affecting to the study outcome (i.e. eating disorder) are excluded using the same question forms used by the dietician for the obese patients.

Echo-planar imaging (EPI) protocol with Philips Gyroscan Intera 1.5T scanner will be used. Functional and anatomical volumes are collected with Philips Gyroscan Intera 1.5T CV Nova Dual scanner. High-resolution, anatomical images (1 mm^3 resolution) will be acquired using a T1-weighted sequence (TR=25 ms, TE=4.6 ms, flip angle 30°, scan time 376 s). Whole-brain functional volumes are acquired using blood oxygenation level dependent (BOLD) -weighted EPI sequence (TR=2998 ms, TE=50 ms, flip angle 90°, FOV=192 mm, matrix=64x64, bandwidth=62.5 kHz, slice thickness=4.0 mm, gap between slices=0.5 mm, 30 interleaved slices acquires in ascending order) sensitive to BOLD contrast. Manual responses will be acquired with a MRI compatible button box.

The stimuli consists of digitalized full-colour photographs depicting

- I. Appetizing, high-calorie foods (e.g. chocolate cake, sweets)
- II. Bland, low-calorie foods (e.g. cabbage, lentils)
- III. Non-food objects (e.g. cars, tools)

Fifty images from each category will be used. Stimulus presentation will be controlled with Presentation computer program (Neurobehavioral Systems Inc.) Stimuli are projected from an LCD projector onto a non-magnetic screen mounted at the foot of the scanner tube, and an angled mirror reflects the images on the screen to the participants' field of vision.

The experiment will run with a classic blocked (box-car) design. Appetizing foods, bland foods and non-food objects will be presented in separate 15 second -blocks that consist of presentation of five pictures from the respective category. A 15 s rest period (fixation) will be intermixed between the stimulation blocks to reduce the activation of the reward systems back to baseline level and to enhance the power of the design. Each stimulus will be displaced slightly to the left or to the right from the centre of the screen and the participant has to detect the direction of the displacement and respond with a button press. This ensures that the participant has to pay attention to the stimuli. A total of 10 blocks per condition will be run, and the order of the blocks will be counterbalanced across the participants. The experiment lasts about 15 minutes. After the experiment, the participants will rate how appetizing the food stimuli were, using a scale ranging from 1 (not appetizing at all) to 10 (extremely appetizing).

SPM5 software (www.fil.ion.ucl.ac.uk/spm/software/spm5) is used for the data analysis (84). First, functional images are sinc (sine cardinal) interpolated in time to correct for slice time differences and realigned to the first scan by rigid body transformations to correct head movements. Next the images are unwarped and a mean functional image is generated. The mean functional images are inspected for excessive signal dropout. EPI and structural images are co-registered and normalized to the T1 standard template in MNI space (95) using linear and non-linear transformations, and smoothed with a Gaussian kernel with 8 mm FWHM. A random effects model is implemented using a two-stage process of within (first level) and between (second level) –subjects modelling. This random-effects analysis assesses effects on the basis of inter-subject variance and thus allows making inferences from the population from where the participants were selected. For each participant a General Linear Model (GLM) is used to assess regional effects of task parameters on BOLD indices of activation. The model includes four experimental conditions (appetizing foods, bland foods, objects, rest) and effects of no interest (realignment parameters) to account for motionrelated variance. Low-frequency signal drift is removed using a high-pass filter (cut-off 128 seconds) and AR(1) modelling of temporal autocorrelations is applied. The individual voxel-wise tcontrast images are generated using the following contrasts:

- (1) Appetizing vs. bland foods
- (2) Bland vs. appetizing foods
- (3) Appetizing and bland foods vs. objects

These images are subsequently entered into a second-level model, subjected to a voxel-wise contrast and t-test using Gaussian Random Field Theory to assess whether or not the reward systems respond to high and low calorie foods in the experimental and the control group. A mixed ANOVA will be used to assess whether the responses of the reward system are different in the experimental vs. in the control group. The appetizing vs. bland foods contrast is used to assess the activation of the reward system in the experimental groups. The appetizing food vs. objects and bland foods vs. objects contrasts will be used to assess whether the gastric sleeve or gastric bypass surgery reduces the responses to appetizing foods only.

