## **3. OBJECTIVES AND HYPOTHESES**

## 3.1. Objectives:

The objectives of this study are to measure effect of weight loss and the possible differences between sleeve gastrectomy and gastric bypass:

- 1. On whole-body and fasting free fatty acid metabolism in myocardium, skeletal muscle, liver, pancreas, intestine, bone, brain and subcutaneous and visceral fat.
- 2. On total body fat and abdominal fat distribution & abdominal fat volumes
- 3. On liver fat content
- 4. On glycemic control and on biochemical markers (leptin, ghrelin, adiponectin, HDL, LDL, triglycerides, cholesterol, calcium, B12-vitamin, cytokines, bile acids and high sensitivity C-reactive protein).
- 5. On brain white and gray matter volumes and distribution
- 6. On brain activation response to food stimuli before and after surgery
- 7. On the two specific neurotransmitter systems, dopamine and opioid
- 8. On correlation between brain activation to food stimuli and hormonal changes especially of the gastrointestinal peptides (e.g. ghrelin)
- 9. On correlation between the subjective feelings of hunger and brain activation
- **10.** On markers of bone metabolism (Vitamin D, PTH, S-Ctx, bsAP, PINP and osteocalcin) and bone mineral density
- 11. On quantitative and metabolic changes in the bone marrow fat

We also aim:

- **12.** To take DNA samples for further investigation on genetic markers related to cardiovascular diseases, type 2 diabetes and obesity risk factors as a part of CMGene-study
- 13. To investigate the effect of morbid obesity on the histology and thus take biopsies
  - a. During endoscopy from gastric mucus, duodenum, antrum and corpus
    - b. During surgery from liver, abdominal subcutaneous and visceral fat
- **11.** To investigate the effect of morbid obesity and the surgery-induced weight loss on the histology of abdominal subcutaneous adipose tissue by taking a biopsy from abdominal adipose tissue
- 12. To measure the effects of bariatric surgery on gene and protein expression in these tissue biopsies
- 13. To compare the general risk factors between sleeve gastrectomy (SG) and gastric bypass
- 14. To obtain information about the hormonal benefits and long-term results of SG
- 15. To investigate the effects of bariatric surgery on intestinal perfusion and metabolism.
- **16.** To investigate the effects of bariatric surgery on the rate of bone turnover and bone quality using paired bone biopsies
- **17.** The rate of bone turnover (bone biopsy),

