### 6.4.5 Visual stimulation for fMRI

During the primary fMRI experiment, anticipatory food-related reward activity will be induced by showing the participants alternating 16s blocks of appetizing, high-calorie and bland, low-calorie food pictures. Periodically the participants are asked to evaluate their i) hunger level and ii) heart rate. In two control experiments, rewarding and nonrewarding control stimuli (bodies, faces and objects) will be presented using a similar design. All experiments will last approximately 12 minutes. Additional resting state block of 10 minutes will also be included. fMRI will be performed pre- and postoperatively. In the preoperative scan, testing for an interaction between the food type (appetizing vs. bland) and group (patients vs. controls) will reveal the components of the reward circuit that show enhanced responses to appetizing foods in obesity. BOLD signal changes due to viewing appetizing and bland foods will be correlated with striatal  $D_2R$  density.

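### The protocol names a sleeve-versus-bypass difference as part of the main fMRI interest, but none of its listed fMRI analyses tests it

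*Protocol*

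**What the plan says.** **The question.** Section 6.3.2.2 gives the main interest of the fMRI work in two parts: whether surgery specifically lowers responses to appetizing food, and "is there a difference in responses between the two surgical procedures". Section 3.1 opens its objectives with the aim to "measure effect of weight loss and the possible differences between sleeve gastrectomy and gastric bypass", and item 6 under that opening is the brain response to food stimuli. Section 5.1 randomises 20 patients to each operation; the 20 lean controls are recruited, not randomised.

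**The analyses.** Section 6.3.2.2 then describes the second-level model and gives each test a purpose:

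- voxel-wise t-tests of whether the reward systems "respond to high and low calorie foods in the experimental and the control group";
- a mixed ANOVA to "assess whether the responses of the reward system are different in the experimental vs. in the control group";
- the appetizing-versus-bland contrast, for activation in the experimental groups;
- the two food-versus-objects contrasts, to "assess whether the gastric sleeve or gastric bypass surgery reduces the responses to appetizing foods only".

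Section 6.4.5 adds, for the preoperative scan, "testing for an interaction between the food type (appetizing vs. bland) and group (patients vs. controls". Section 6.4.7 predicts raised responses in patients before surgery that disappear afterwards. Section 6.4.1 covers stimuli, preprocessing and the general linear model and lists no group or visit comparison. Section 12.2 leaves the statistical analysis open in general terms. Section 12.1 gives alpha as 0.05.

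**The concern.** One of the two questions called the main interest has no test assigned to it, although the same section specifies the rest of the fMRI analysis down to the smoothing kernel and high-pass filter. The group factor in the mixed ANOVA is patients against controls, and so is the interaction in section 6.4.5.

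The omission matters because sleeve versus bypass is the only comparison that randomisation protects. Patients and controls differ in far more than weight, and a before-after change in patients mixes the operation with time, repeat scanning and everything else that happens over six months. If the listed tests are followed as written, the randomised comparison is not made. If someone fills the gap by looking at each operation separately, the result answers a different question with an uncontrolled error rate.

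**Working it through.** **Step 1. Match each listed test to the hypothesis it tests.**

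| Listed analysis | Section | Null hypothesis |
|---|---|---|
| t-tests in the experimental and control group | 6.3.2.2 | no response in that group |
| Mixed ANOVA | 6.3.2.2 | patients equal controls |
| Appetizing versus bland, experimental groups | 6.3.2.2 | no differential activation |
| Each food type versus objects | 6.3.2.2 | surgery does not reduce the response |
| Food type by group, preoperative scan | 6.4.5 | same food effect in patients and controls |

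No row has the null that the change is equal after sleeve and bypass.

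**Step 2. The plan's own figure.** Section 12.1 states 20 + 20 patients and 20 controls at alpha 0.05. It gives no effect size, SD, power or sidedness, so the number cannot be reproduced. Solving backwards for two arms of 20 at two-sided 0.05 (sidedness assumed), the detectable standardised difference is 0.89 SD at 80% power and 1.03 SD at 90% by the normal approximation, or 0.91 and 1.05 by the exact t calculation.

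**Step 3. What separate within-arm tests would do if used to judge a procedure difference.** Assume two independent arms of 20, equal variance, the same true pre-to-post change in both, one region or measure, and power p for each within-arm test. The chance that the first arm is significant and the second is not is p(1-p), and the reverse is equally likely, so

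P(exactly one arm significant) = 2p(1-p).

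- p = 0.05 (no effect in either arm): 2 × 0.05 × 0.95 = 9.5%
- p = 0.50: 2 × 0.50 × 0.50 = 50%, the maximum
- p = 0.80: 2 × 0.80 × 0.20 = 32%
- p = 0.95: 2 × 0.95 × 0.05 = 9.5%

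To relate p to effect size, take the paired t-test with n = 20 (19 degrees of freedom, noncentrality d × √20, two-sided 0.05), where d is the mean change divided by the SD of the change. The d values are assumptions, because the protocol gives none.

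| d | p | 2p(1-p) | Simulated |
|---|---|---|---|
| 0.30 | 0.247 | 37% | 37.3% |
| 0.46 | 0.497 | 50% | 50.0% |
| 0.66 | 0.799 | 32% | 32.0% |
| 0.80 | 0.924 | 14% | 14.1% |
| 1.00 | 0.989 | 2% | 2.2% |

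The simulation used 100,000 runs per setting.

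**Step 4. The direct test.** In the same simulation, a two-sample t-test on the individual changes, 20 versus 20, rejected in 4.95% to 5.11% of runs whatever the common effect. Its power, by exact t, is 34% for a difference of 0.5 SD of the change, 69% for 0.8 SD and 79% for 0.9 SD. A non-significant result would therefore not show that the operations act alike, and the confidence interval is needed.

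**The case against.** The strongest reply is that this is an omission which an analysis plan could fill. Section 12.2 excludes nothing, section 6.3.2.2 does not call its list exhaustive, and a mixed ANOVA could carry a three-level group factor. The section also refers once to experimental groups in the plural. Nor is the gap peculiar to fMRI: the objectives in section 3.1 promise the sleeve-bypass comparison for many outcomes, and section 6.4.6 on receptor PET likewise names only obese-versus-lean and pre/post tests.

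Much of this stands. It is why the point is a mismatch to repair and not a claim that the comparison has been ruled out. It does not remove the mismatch: section 6.3.2.2 states two questions, assigns named tests to named purposes, sets the group factor as patients against controls, and leaves the second question without a test. A general sentence in section 12.2 does not supply one.

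A reader might go further and infer that the protocol intends to judge the procedures by significance in one arm and not the other, with a false-positive rate of about one half. The documents do not support that. No section prescribes such a rule. The t-tests speak of one experimental group, so patients may be pooled, and the phrase about sleeve or bypass surgery can be read as pooled, arm by arm, or with arm as a factor. One half is also only the worst case, at within-arm power near 50%; with high power the figure falls towards zero. Rates at a stricter voxel threshold would rest on a value that the protocol does not state.

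**Conclusion.** The point holds as an internal mismatch. A sleeve-bypass difference in fMRI response is part of the stated main interest and falls under a stated objective, yet none of the group-level fMRI analyses set out in sections 6.3.2.2 and 6.4.5 tests it. Followed as written, they would leave the only randomised comparison untested.

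The percentages describe a risk if the open wording were read arm by arm; they are not the error rate of a planned rule. On that reading, with equal true effects, exactly one arm would be significant in at most 50% of trials, in 32% at 80% within-arm power and in 9.5% at 95%, against 5% for a direct test. These figures rest on independent, equal arms of 20, equal variance, a single measure, two-sided 0.05 and assumed power. The omission itself rests on none of these assumptions.

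**What to change.** Add to the second-level analysis in section 6.3.2.2 wording to this effect:

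> The sleeve-bypass question is tested in patients as randomised by the procedure-by-visit interaction on the appetizing-versus-bland contrast (equivalently, a two-sample comparison of individual post-minus-pre contrast images). The same comparison on appetizing versus objects and on bland versus objects shows which food type drives any difference. The estimate and 95% CI are reported for the named reward regions. Significance within one arm and not the other is not used to infer a difference between procedures.

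The objects contrasts are needed because appetizing-versus-bland alone cannot show whether a difference comes from one food type or the other; section 6.3.2.2 already uses them for its question on appetizing foods. The regions should be listed once, since sections 3.2.3 and 6.4.7 name slightly different sets.

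The cost is wording and a few extra contrasts on scans already planned. No new data, visits or patients are needed.
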